4. OBJECTIVES*

The Specific Aims for Phase 2 have been modified from the original submission with approval from the program officer at NIDA. Updated Aims are as follows:

Phase 1, Aim 1: To develop the OARS+CM platform. User-centered design principles will be employed to enhance the existing OARS software to produce OARS+CM. This will culminate in a proof-of-concept study of up to 20 individuals with OUD and their providers/clinicians whose feedback and experiences will be used to iteratively improve the interface and features. The usability criterion will be reached when \geq 3 participants in a row are able to use the program without staff assistance (with on-device support if needed, as intended) and no more substantive improvements are needed. We will also assess acceptability, and rates of treatment initiation and adherence (attending therapy, drug urine/saliva tests).

Phase 2, Aim 1: To assess the efficacy of OARS+CM in promoting MOUD treatment initiation. Using a randomized controlled trial (N=102 randomized), the efficacy of the OARS+CM (n=51) in promoting MAT initiation will be tested against TAU with MyMAT (an educational mobile app) (n=51).

H1: OARS+CM will result in greater MOUD treatment initiation from acute care settings than TAU with MyMAT.

Phase 2, Aim 2: To assess efficacy of OARS+CM in promoting transition from MOUD Initiation to maintenance.

H2: OARS+CM will result in greater rates of sustained abstinence for 6 months after the index visit.

H3: MOUD therapy attendance will be increased such that OARS+CM >TAU with MyMAT.

Phase 2, Aim 3: To evaluate costs. Exploratory data on cost-effectiveness, cost avoidance and cost savings through reduced acute care visits between conditions will be collected and analyzed.

This submission is currently seeking approval for Phase 2 following successful completion of Phase 1, as the NIH will only fund Phase 2 if Phase 1 is successful. All materials for Phase 2 in this submission outline what has occurred since Phase 1 was completed successfully. Any changes to Phase 2 material have been revised and are being submitted to the IRB as a modification for review and approval when appropriate.

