6. INCLUSION AND EXCLUSION CRITERIA*

Inclusion and Exclusion Criteria: See grant: "HUMAN PARTICIPANTS PROTECTION" (p.17) for details. The Overall Study Design, Study Population and Randomization, and Interventions for Phase 2 have been modified from the original submission. Updated Overall Study Design, Study Population and Randomization, and Interventions are as follows:

Overall Study Design: This Fast-Track STTR includes a small proof of concept pilot study followed by a randomized controlled trial (RCT) with two conditions: 1) treatment as usual (TAU) with MyMAT, and 2) the OARS + CM. This study will use recruitment and study enrollment procedures successful in our prior SUD research (refer to Biosketches). Participants will be individuals with OUD presenting to acute care settings. They will complete a screening survey to assess for minimal eligibility criteria and confirm their interest. Once confirmed, research staff will obtain written informed consent and enrolled in the study. Participants will be randomized to one of two conditions described above. The study period begins at enrollment during their index acute care visit. Follow-up surveys and tracking through the mobile application (OARS+CM) and review of all relevant healthcare records will occur at 1, 3, and 6 months after enrollment. For scientific rigor, biochemical verification of abstinence from opioids

will be obtained from outpatient treatment records. Self-reported use will also be obtained through structured follow-up assessments.

Study Population and Randomization: We will randomly assign N=102 individuals with OUD meeting minimal eligibility criteria to one of two conditions using REDCap, allocated 1:1 to the two conditions.

Interventions:

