5. Patient will not receive any follow up calls after the hospital visit but will have their use of the OARSCM mobile application and engagement with treatment as tracked by the OARSCM mobile application monitored for 4 weeks. Participation in this study will last about 4 weeks once the patient has started MAT treatment. After these 4 weeks, the participants will be informed that their 4-week participation has now ended and that we appreciate their participation. They will also be informed that new information related to their appointments, appointment attendance, appointment engagement and tox results will not be entered into their OARSCM mobile application profile. However, they will be able to view this DATA that had been previously entered throughout the 4-weeks. They will continue to have access to their OARSCM mobile application account in order to use their unredeemed Spins, Prizes, and eGift cards for a short time. During enrollment, patient participants will be given a handout on how to uninstall the application if they no longer want the application on their smart phone after participation. See grant: "RESEARCH STRATEGY" (p. 8). See grant: "APPENDIX" for screenshot of patient notification that their 4-week participation has now ended and handout of how to uninstall the mobile application.

Phase 2: Aims 1 and 2 (Efficacy of OARSCM): 102 patients randomized to 1 of 2 groups If the patient agrees to participate:

- 1. Participants (acute care patients who meet eligibility criteria and complete consent process, see section 30. Consent Process) will be randomized to either TAU (with MyMAT) or OARS mobile application plus contingency management (OARSCM).
- 2. Participants will complete an interview assessment during their current medical visit. It takes about 20-30 minutes to complete. They will be asked to provide a urine sample. It will not interfere with their care.
- 3. Participants will be provided a warm handoff to a community-based MOUD treatment provider. All participants will be eligible to receive standard MOUD treatment per treatment as usual at the site they are referred to. If they are randomized to OARSCM, they will use the mobile application to track treatment progress and have the potential to earn prizes for engaging with the application throughout treatment.

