25. LOCAL NUMBER OF SUBJECTS

Phase 1 Aim 1 (Develop OARSCM): 30 individuals with OUD and 30 providers/clinicians will be recruited to provide feedback to improve the interface and features.

Phase 2 Aims 1 & 2 (RCT of OARSCM): 102 patients will be enrolled and randomized into OARS+CM (n=51), or TAU with MyMAT (n=51) to determine efficacy of OARSCM. See grant: "RESEARCH STRATEGY" (p12) "Procedures" for further details.

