Phase 2, RCT. will proceed with the intent-to-treat sample. Initial analyses will compare groups on baseline and demographic variables using chi-square test (for categorical variables) and analysis of variance (for continuous variables). Variables that significantly differ between groups or are theoretically important, such as pain and other (non-opioid) substance use disorder will be used as covariates in multivariate analysis, when appropriate. For end-of-treatment outcomes, analysis will compare groups via chi-square, Kruskal-Wallis test, and analysis of variance (ANOVA) or analysis of covariance (ANCOVA) tests, as appropriate. Evaluation of changes in outcomes through the follow-up period will occur with hierarchical mixed models specified for dichotomous or continuous outcomes. To use the mixed effect modeling analysis in assessing intervention effect, an interaction term (intervention group by time) will be included together with other covariates (e.g., age, ethnicity, chronic pain, anxiety, trauma history, utilization of psychiatric or medical services). A significant beta coefficient of the interaction term at $p < .05$ level will be used as evidence supporting the intervention effect. Analysis of change scores can analyze variables that cannot be normalized.

The Primary Aim 1 is to assess the efficacy of OARS+CM in promoting Suboxone treatment initiation.

The primary outcomes will be the proportion of participants who schedule a Suboxone treatment intake visit, and the proportion of participants who complete the Suboxone intake visit to start outpatient treatment. These outcomes are usually non-normally distributed and will be analyzed accordingly. We will assess the effect of the intervention using generalized linear mixed model, controlling for the dependence of repeated measures and the clustering effects.

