Sample size justification. We use the proportion of participants who complete the Suboxone intake to start treatment as the calculating indicator. Based on the findings from a large randomized clinical trial on MAT treatment for opioid dependence after an acute care visit,¹⁵⁸ we estimate the proportion of patients who will initiate MAT at baseline is about 35%. We hypothesize that OARS will increase the rate by 25% and OARS+CM will increase the rate by 50%. Using G-Power program (proportions procedure) with $\alpha=0.05$, $N=150$ (50 each group), the calculated statistical power is >0.80 for the comparisons between TAU and OARS, TAU and OARS+CM, and OARS and OARS+CM.

Aim 2 is to assess the efficacy of OARS+CM for increasing Suboxone treatment adherence and abstinence outcomes. Main outcomes will be the percentage of opioid-free urine toxicology tests, and the percentage of group/individual therapy sessions attended. Secondary outcomes will be the longest duration of abstinence (LDA) outcome, measured at month 1, month 3 (end of study period) and month 6 (end of follow-up period), and sustained abstinence from Suboxone start through each follow-up. LDA and sustained abstinence will be as a composite of the greatest number of days with consecutive negative urine samples and self-reported no use; a composite of biochemical evidence and subjective report is needed because urine tests are too infrequent in the clinical setting to rigorously determine sustained abstinence based solely on biochemical evidence. Sustained abstinence and LDA are usually non-normally distributed and will be examined accordingly. We will assess the effect of the intervention using linear mixed model, controlling for the dependence of repeated measures and the clustering effects.

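### The SAP's power statement belongs to a three-arm, N=150 design; nothing supplied gives power for the two arms of 51 being randomised, and effect scale and sidedness are not stated

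*SAP*

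**What the plan says.** The SAP's sample size justification (Phase 2, RCT) bases power on completed Suboxone intake. It takes a 35% rate without the intervention and continues: "We hypothesize that OARS will increase the rate by 25% and OARS+CM will increase the rate by 50" per cent. With alpha 0.05 and 150 patients, 50 in each of three groups, it concludes that "the calculated statistical power is >0.80 for the comparisons between TAU and OARS, TAU and OARS+CM, and OARS and OARS+CM".

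The protocol describes a different trial, and does so consistently:

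- Section 4 (Objectives, Phase 2 Aim 1): "Using a randomized controlled trial (N=102 randomized), the efficacy of the OARS+CM (n=51) in promoting MAT initiation will be tested against TAU with MyMAT", with 51 in that arm as well.
- Section 6 (Study Population and Randomization): 102 individuals, "using REDCap, allocated 1:1 to the two conditions".
- Section 11 (Procedures, Phase 2 Aims 1 and 2): "102 patients randomized to 1 of 2 groups".
- Section 25 (Local Number of Subjects): "102 patients will be enrolled and randomized into OARS+CM (n=51), or TAU with MyMAT (n=51) to determine efficacy of OARSCM".

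Under Primary Aim 1 the SAP names two primary outcomes: scheduling an intake visit, and "the proportion of participants who complete the Suboxone intake visit to start outpatient treatment". Only the second is used for power. Significance is set at p < .05 throughout, and neither document says whether that is one- or two-sided.

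**The concern.** The power claim is current SAP text, but it describes arms and comparisons that the trial does not have. There is no OARS-only group, so TAU vs OARS and OARS vs OARS+CM cannot be run. The control is now usual care plus an educational app. Neither supplied document gives power for 51 vs 51.

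The remaining comparison cannot simply be read off the old paragraph, because its effect size has two meanings. An increase of 50% on 35% is 85% in percentage points and 52.5% as a relative change. These imply very different trials, and a null result cannot be interpreted without knowing which effect the trial was sized to detect. Section 32 of the protocol says the data will support a 510(k) submission, so the sample size justification should match the design.

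**Working it through.** **Inputs.** Control rate 0.35, alpha 0.05 and 50 per group come from the SAP sample size justification; 51 per arm comes from protocol sections 4 and 25. The two readings of the assumed increases are:

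- percentage points: OARS 0.35 + 0.25 = 0.60; OARS+CM 0.35 + 0.50 = 0.85
- relative: OARS 0.35 × 1.25 = 0.4375; OARS+CM 0.35 × 1.50 = 0.525

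**Formula.** Two-proportion z test with pooled null variance, n per arm, p̄ = (p1 + p2)/2:

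power = Φ{ [ |p2 − p1| − z·√(2p̄(1−p̄)/n) ] / √[ (p1(1−p1) + p2(1−p2))/n ] }, with z = 1.960 two-sided or 1.645 one-sided.

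**Step 1: the SAP's own figure (n = 50).** Example: TAU vs OARS, percentage points, two-sided. The null SE is √(2 × 0.475 × 0.525/50) = 0.0999 and the alternative SE is √[(0.2275 + 0.24)/50] = 0.0967. So (0.25 − 1.960 × 0.0999)/0.0967 = 0.56, and Φ(0.56) = 0.71.

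| Reading | Sides | TAU vs OARS | TAU vs OARS+CM | OARS vs OARS+CM |
|---|---|---|---|---|
| Percentage points | 2 | 0.71 | >0.99 | 0.81 |
| Percentage points | 1 | 0.81 | >0.99 | 0.89 |
| Relative | 2 | 0.14 | 0.42 | 0.14 |
| Relative | 1 | 0.23 | 0.55 | 0.22 |

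Power above 0.80 for all three is reproduced only with percentage points and a one-sided test, and then only by uncorrected approximations (pooled z, unpooled z or arcsine). For TAU vs OARS, the one-sided exact chi-square gives 0.799, the continuity-corrected z 0.75 and Fisher's test 0.74. The relative reading never exceeds about 0.56 for any comparison, one- or two-sided.

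**Step 2: the comparison being run (n = 51, two-sided).**

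- 35% vs 52.5%: (0.175 − 1.960 × 0.0982)/0.0967 = −0.18, power 0.43 (exact chi-square 0.46, Fisher 0.38).
- 35% vs 85%: (0.50 − 1.960 × 0.0970)/0.0834 = 3.71, power >0.99 by every method.

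**Step 3: sample size implied by each reading (80% power, two-sided).**

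n = { [1.960·√(2p̄(1−p̄)) + 0.842·√(p1(1−p1) + p2(1−p2))] / |p2 − p1| }²

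This gives 125 per arm for 52.5% and 14 per arm for 85%. Neither is close to 51.

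**Step 4: what 51 per arm can detect.** Solving the power formula for p2 at 80% power against 35% gives 62.4% (pooled z), 61.7% (unpooled z), 61.6% (exact chi-square) or 63.6% (Fisher), a difference of 27 to 29 points. At 62.5% the pooled z power is 0.80.

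**Step 5: sensitivity to loss.** The documents give no attrition figure, so 0, 10 and 20% equal loss are assumptions.

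| n per arm | Power at 52.5% | Power at 62.5% | Power at 85% | Detectable rate (80% power) |
|---|---|---|---|---|
| 51 | 0.43 | 0.80 | >0.99 | 62.4% |
| 46 | 0.39 | 0.76 | >0.99 | 63.8% |
| 41 | 0.36 | 0.71 | >0.99 | 65.5% |

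**The case against.** The strongest reply is that the SAP's own result indicates which scale was meant. The relative reading cannot produce power above 0.80 for any comparison, while percentage points come close two-sided and succeed one-sided. On that reading the retained comparison has power above 0.99, even at 41 per arm, and the one comparison that fails two-sided (TAU vs OARS, 0.71) is no longer run. This stands. The 0.43 figure is something the wording allows, not something the stated power supports, and it should not be read as evidence of an underpowered trial.

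Three further points have some force:

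- Two-sided testing is assumed here. It fits the planned chi-square tests at p < .05, but the SAP does not say so, and the sponsor should confirm it.
- Attrition may matter little for this endpoint. The protocol's section 11 schedule monitors intake completion, the same section has healthcare records reviewed for every participant, and the analysis is intention-to-treat.
- The protocol refers to grant pages that were not supplied, and section 4 says the Phase 2 aims were modified with the funder's agreement. A justification for 102 may exist there.

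None of this puts a valid power statement for 51 vs 51 into the supplied documents. The percentage-point reading also leaves 51 unexplained, since it needs only 14 per arm.

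**Conclusion.** The point holds and should be fixed. The SAP's N of 150, its three arms and two of its three power claims do not belong to the trial in the protocol. That the paragraph was carried over from the design before modification is an inference from protocol section 4; the contradiction stands without it.

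For the retained comparison, two-sided power is above 0.99 or about 0.43 depending on an unstated scale, and the first fits the SAP's claim better. The finding is that power is not validly stated for the design being run, not that the trial is too small. The figures assume a 35% control rate, complete ascertainment except where loss is shown, no clustering, and no adjustment for having two primary outcomes. The conclusion covers the supplied documents only.

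**What to change.** Replace the SAP's sample size paragraph, leaving N at 102. Suggested text:

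*With 51 participants per arm (OARS+CM vs TAU with MyMAT), two-sided alpha 0.05 and 35% of controls completing the intake visit, the trial has 80% power to detect an OARS+CM completion rate of about 62.5% (27 to 28 percentage points, pooled z test).*

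Then:

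- Add one sentence giving the assumed OARS+CM rate as an absolute percentage with its power: 85% (>0.99) if percentage points were meant, 52.5% (about 0.43) if relative. The 62.5% is a detectable rate derived from 51 per arm and should not be presented as the planning assumption.
- Confirm that alpha is two-sided. If not, recompute the figures.
- State the attrition allowance, or that intake completion is ascertained for all randomised patients.
- State that power refers to completed intake, one of the two primary outcomes.
- Delete the OARS-only arm and the N=150 comparisons.

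The cost is SAP wording only: no extra patients, visits or data. The sponsor must say which scale was meant. If it was relative, the stated power falls to about 0.43.

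### The SAP does not test H2 as the protocol states it: sustained abstinence is secondary, counted from Suboxone start, measured in days, and given no binary model

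*SAP*

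**What the plan says.** Protocol section 4 (Objectives) gives Phase 2 Aim 2 two hypotheses. H2 is that "OARS+CM will result in greater rates of sustained abstinence for 6 months after the index visit". H3 is that "MOUD therapy attendance will be increased such that OARS+CM >TAU with MyMAT".

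The SAP's Aim 2 paragraph sets a different order. "Main outcomes will be the percentage of opioid-free urine toxicology tests, and the percentage of group/individual therapy sessions attended". Below these it lists two secondary outcomes: longest duration of abstinence (LDA) at months 1, 3 and 6, and "sustained abstinence from Suboxone start through each follow-up". Both share one definition: "LDA and sustained abstinence will be as a composite of the greatest number of days with consecutive negative urine samples and self-reported no use". On distribution it says: "Sustained abstinence and LDA are usually non-normally distributed and will be examined accordingly". The next sentence names the model: "We will assess the effect of the intervention using linear mixed model".

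Elsewhere the SAP says that analyses use the intent-to-treat sample (opening and Phase 2 RCT paragraphs). It provides for mixed models for dichotomous as well as continuous outcomes, and it names a generalized linear mixed model for the Aim 1 proportions. No sentence assigns a binary model to H2 or makes 6-month sustained abstinence the main test of Aim 2.

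**The concern.** A hypothesis is tested only if the analysis plan contains its outcome, on its scale, from its time origin, in its population. H2 loses all four in the SAP's Aim 2 paragraph.

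The time origin does the most damage. Starting Suboxone happens after randomisation and is what the intervention is meant to change (H1). An outcome counted from that start has no defined value for non-starters. If they drop out of the analysis, the arms being compared have been selected by an effect of treatment, and the comparison is no longer randomised.

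The rank and the scale matter too. The trial could finish with a result for percent opioid-free urines, a result for days abstinent, and no agreed answer to the abstinence question that the protocol poses. Protocol section 32 says that the data will support a 510(k) submission, so it should be clear in advance which result answers H2.

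**Working it through.** **1. The two texts side by side**

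| Feature | Protocol, H2 | SAP, Aim 2 paragraph |
|---|---|---|
| Rank | One of two Aim 2 hypotheses, and the only one on abstinence | Secondary, beside LDA |
| Scale | A rate, so yes/no per participant | Greatest number of consecutive days, shared with LDA |
| Clock starts | Index visit | Suboxone start |
| Time point | 6 months | Through each follow-up (months 1, 3, 6) |
| Model | None stated | Linear mixed model; dichotomous models allowed only in the general text |

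The mismatch is complete at this step and needs no arithmetic. Of the SAP's two main outcomes, sessions attended corresponds to H3. Only H2 is displaced.

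**2. How many participants the Suboxone-start clock could leave without a value**

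Inputs: 51 per arm (protocol sections 4 and 25), a control initiation rate of 35%, and an increase of 50% with OARS+CM (SAP, sample size justification). The SAP does not say whether the increase is absolute or relative. Assumption: completing intake stands for starting Suboxone.

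- TAU with MyMAT: 0.65 × 51 = 33.2 non-starters.
- OARS+CM, absolute reading (35% + 50 points = 85%): 0.15 × 51 = 7.7.
- OARS+CM, relative reading (35% × 1.5 = 52.5%): 0.475 × 51 = 24.2.
- Total: 33.2 + 7.7 = 40.9, or 33.2 + 24.2 = 57.4. That is about 41 to 57 of 102 (40% to 56%).

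The gap between arms (33 against 8, or 33 against 24) is the selection problem: the more H1 succeeds, the less alike the two sets of starters become.

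**3. The plan's own power figure**

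The only power figure, above 0.80, is for intake completion with 50 in each of three groups. With p̄ the mean of p₁ and p₂ and q = 1 − p,

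power = Φ{ [ |p₁ − p₂|√n − z√(2p̄q̄) ] / √(p₁q₁ + p₂q₂) }.

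On the absolute reading (35%, 60%, 85%), one-sided 0.05, this gives 0.812 (TAU v OARS), above 0.99 (TAU v OARS+CM) and 0.885 (OARS v OARS+CM), so the figure reproduces. Two-sided, the first falls to 0.713. None of this concerns H2, for which no rate and no power are given.

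As an illustration only, the same formula with 51 per arm, two-sided 0.05 and 80% power gives these detectable differences for *assumed* control rates of sustained abstinence:

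| Assumed control rate | Difference needed |
|---|---|
| 5% | 19.5 points |
| 10% | 22.5 points |
| 20% | 25.8 points |
| 40% | 27.4 points |

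**4. Multiplicity, if any positive abstinence result were accepted for H2**

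For k independent tests at 0.05 the chance of at least one false positive is 1 − 0.95^k. For equally correlated normal statistics it was found by numerical integration. The correlations are assumed.

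| Tests counted | ρ = 0 | ρ = 0.5 | ρ = 0.7 |
|---|---|---|---|
| 3 (percent opioid-free, LDA, sustained abstinence) | 14.3% | 12.5% | 10.9% |
| 7 (percent opioid-free, and the other two at three times each) | 30.2% | 23.0% | 17.8% |

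**The case against.** An SAP may rank outcomes as it sees fit, and protocol section 10 refers endpoints to grant pages outside these documents, so the hierarchy may be settled there. Both points are fair. Neither removes the conflict between H2 and the SAP; they mean that either text could be the one to change.

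The linear model is also less odd than it looks. The SAP treats sustained abstinence as a day count, so within the SAP the model is applied to a numeric outcome. A reader might infer that the plan has no suitable model for H2. The documents do not support that: dichotomous mixed models are provided for in general, and the Aim 2 paragraph promises to take account of non-normality. What stands is that no binary model is assigned to H2.

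A reader might also infer seven separate abstinence tests and a false-positive chance of 30%. The SAP handles months 1, 3 and 6 as repeated measures within a mixed model, so three outcomes is at least as plausible a count. LDA and sustained abstinence share a definition, so independence is implausible. The SAP also allows separate end-of-treatment tests, so the count is not fixed either way.

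Nor does any sentence say that percent opioid-free urines will be used to claim H2. That risk comes from silence, not from a stated intention.

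Finally, an index-visit clock has its own difficulty. Protocol Table 1 admits patients presenting with opioid intoxication, so the counting rule around day 0 must be written down. A single value per participant also gives up the likelihood-based handling of missing data described in the SAP's opening paragraph. Both points stand and are taken into the fix.

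**Conclusion.** The point holds. Followed as written, the SAP's Aim 2 paragraph does not test H2: it changes the outcome's rank, scale and clock, and leaves its model ambiguous. This rests on the text alone.

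The serious part is the clock. The figure of about 41 to 57 of 102 without a defined value assumes that the SAP's planning rates hold and that intake completion stands for Suboxone start. A rule giving non-starters a value would remove the gap, but the SAP states none.

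The false-positive figures (about 11% to 14% for three outcomes, 18% to 30% for seven, at correlation 0.7 down to 0) depend on an assumed count and correlation. They are a range and not a property of the plan. The conclusion does not need them.

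The primary aim is unaffected. H2 is nevertheless a pre-stated efficacy hypothesis, and this should be corrected before outcome data are examined.

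**What to change.** In the SAP's Aim 2 paragraph:

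- Define the H2 outcome as a yes/no status, sustained abstinence through month 6 counted from the index visit, for every randomised participant. State how opioid use at or around the index visit is counted.
- State a rule for participants who never start Suboxone, and one for missing urine or self-report data. Protocol section 6 takes biochemical verification from outpatient treatment records, so non-starters may have little or no urine data.
- Name this outcome as the single test of H2.
- Analyse it with a binary-outcome model, for example logistic regression with one value per participant. Keep covariates few if events are few.
- Keep percent opioid-free urines and LDA as Aim 2 outcomes if wanted, but say that they will not be used to claim H2.

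If the sponsor prefers the SAP's present ranking, reword H2 to match it. The Suboxone-start clock still needs correcting, because the intent-to-treat conflict remains.

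The cost is wording. The protocol's schedule already lists the Timeline Followback and urine toxicology at month 6, and the sample size does not change. The sponsor should accept, and preferably state, that 51 per arm can detect only large differences in a yes/no abstinence outcome.
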